We plan to conduct a randomized control trial with 10,000 participants. Participation will last for a minimum of 4months and maximum of 8 months, depending upon COVID-19 case rates. Half of participants will be randomized to the control group and continue their existing testing and healthcare practices. The remaining participants will be randomized into the intervention arm. Participants in the intervention will receive one Cue Cartridge Reader for the duration of the study and up to 10 Cue COVID Molecular tests per month for their own

use and to share with others who could expose them to COVID-19 (e.g. close contacts). In the case that a Cue Flu+COVID Molecular Test is available through FDA EUA or other authorization, participants may be provided this multiplex test in lieu of the Cue COVID Molecular Test.

[figure not shown]
Table 1. Summary of Study Arms

Study Arm	Number of participants	COVID-testing practice
Control	5,000	None within this study
Intervention Arm	5,000	10 Cue tests per month to participants' for self and close contact use. Option to utilize Cue's telehealth and Rx delivery.

All intervention participants will be asked to test themselves if they are exposed or when symptoms arise. The primary outcome will be the number of hospitalizations that will be assessed from survey and claims data. We will also compare infection rates, ICU admissions, ED visits, deaths and cost of care between the control and intervention group. Our hypothesis is that access to high sensitivity portable molecular testing and subsequent antiviral treatment will significantly decrease hospitalization and thereby the cost of care.

Interested individuals will access the study via the MyDataHelps platform by web or app to complete the eligibility and informed consent process. Within the MyDataHelps experience, participants will complete study activities such as surveys and optional sharing of claims data. Participants who are randomized to the intervention group will have the option to use Cue Care should they test positive for COVID-19. In the case that the COVID Flu+COVID test is available, the intervention group will also have the option to use Cue Care should they test positive for Influenza. Cue Care contracts licensed Healthcare providers to deliver telemedicine and treatment for COVID-19.

Figure 1: Participant Flow

Study Population

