- The number of hospitalizations will be assessed based on survey data. We expect that at least 80% of participants will complete the FINAL SURVEY even if they have been hospitalized.
- The experiment will be run for 4 to 8 months (depending on number of COVID cases), and we expect to have a similar number of COVID-19 cases per month.
- Interim analyses on the number of events and progress towards achieving enough events for a well-powered statistical test significance may be run start at month 1 or later. Determination of ending the study timeline may be based on having sufficient number of COVID cases and/or hospitalization events to achieve statistical power. Importantly, we will utilize data on the total number of events to determine when to

end the experiment; we will not use information on the difference in the number of events between study arms.

Table 2: Sample size (target)

Sample size estimation	Control Arm N=5000	Intervention Arm N=5000
Loss to follow-up / drop-out / failure	5%	5%
Expected total number of COVID-19 positives	540	513
Loss to report: expected ratio of individuals not reporting in survey	20%	20%
Expected total number of COVID-19 positives correctly reported	432	410
Expected total number of reported hospitalizations	102	68
Expected total number reported in ICU	39	26

Given the assumptions of above, we should reach a target of 900 confirmed COVID positive cases reported in the survey or claims (approximately 450 per arm), that we expect to reach in 8 months if the rate of infection remains stable. The statistical power of the test (alpha=0.05) is equal to 0.76, meaning that if all assumptions hold, we have a 76% chance of observing a statistically significant difference in the number of hospitalizations between Control and Intervention arms.

The minimum target is to reach 800 confirmed COVID positive cases (approximately 400 per arm). The corresponding statistical power of the test (alpha=0.05) in this case is less than 0.7, meaning that if all assumptions hold, we have less than a 70% chance of observing a statistically significant difference in the number of hospitalizations between Control and Intervention arms.

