The experiment will proceed for between 4 and 8 months. We will aim to meet the target number of COVID cases (900) before 8 months, however we may decide to end once the minimum number of cases is reached (800) if the national COVID case trends suggest that we will not reach the target number of cases within 8 months. The study length will be re-evaluated if the minimum number of cases is not met within 8 months.

As a secondary output, we will also consider the total cost for the individuals in the two study arms, based on claims data if available.

Risk Management Procedures

Loss of privacy

Participants will be identified by a 10-digit, randomly assigned alphanumeric study ID. Only the investigators and research staff will have access to the patient's fully identified medical information. The information that matches the code to the identifying information will be kept in a safeguarded database that is password protected.

Adverse Events

We do not expect any adverse events to occur. However, unless otherwise required by local regulations, the sponsor (Scripps Research Translational Institute) is responsible for complying with required timelines for any safety reporting obligation to Health Authority (HA), IRB and to any participating (co or sub) investigators, as defined in applicable laws and regulations. The safety reporting responsibilities to HA and IRB are defined in the collaborative research support agreement.

Data Acquisition, Storage and Analysis

All study data will be integrated by CareEvolution via the study app and the Cue Health app and securely transferred to Scripps Research where it will be stored on servers secured with two-factor authentication.

Future research

Participant information will be kept for up to 6 years after completion of this study for future research that has not yet been planned. Individual information after the removal of identifiers such as names, emails or zip codes will be kept indefinitely for future research studies at Scripps Research Translational Institute.

Subject Payment/Costs

There is no cost to the subject for study participation. Reimbursement of up to \$200 will be redeemable through Amazon gift cards.

Estimated Duration of Study

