We had initially planned for each participant to be part of the study for up to 8 months. However, due to the FDA issuing a warning letter regarding Cue Health's COVID-19 test accuracy and calling for discontinuing use of the device in May 2024, we have decided to end the study early. We plan to analyze the data primarily to characterize the effect of the COVID-19 pandemic on the study population. If connected, claims data collection will persist for about three months after participation ends, and data analysis will continue for one to two years following the completion of data collection.

Consent Procedures

Study purpose, methods, materials, risks, benefits, and alternatives will be provided in a detailed onboarding process as well as in the long form consent, both within the MyDataHelps app. Participants will have the ability to reach the study team by phone or email with anything they may need. Those individuals who were recruited by CDER can reach out to the CDER team for technical assistance as needed. Informed consent will be obtained in the app with a digital signature. Participants will be given a copy of their signed consent form.

Data Security

The collection and processing of personal data from participants enrolled in this study will be limited to the data needed to investigate this study's hypothesis and the clinical data typically used as covariates in the analysis of clinical studies. Access to data will be limited to those authorized by Principal Investigators, including CareEvolution and CueHealth. Privacy policies and user agreements

Scripps Research Translational Institute affirms the participant's right to protection against invasion of privacy. Data files are stored on a password-protected computer/database and will be accessible only to the above-listed investigators and research staff. Only the research staff will have the link that can match the code to traditional identifying information. The data sets used for analysis will be coded and not contain information that could be used to identify the patient.

Participant Withdrawal

Participation is voluntary and the participant can discontinue participation at any time without loss of benefits or penalty. A participant who wishes to withdraw consent can make a request through the app during the study period. Any data that has been entered in the database will be included in the analysis of the study. All study activities and data collection will stop at the time of withdrawal.

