Since you enrolled in ImmunoCARE, have you:

	·	
0	Been exposed to a close contact with COVID-19?	[] Yes [] No
0	Contracted COVID-19?	[] Yes [] No
0	Been prescribed medication for COVID-19?	[] Yes [] No
0	Been to Urgent Care due to COVID-19?	[] Yes [] No
0	Been to the Emergency Room due to COVID-19?	[] Yes [] No
0	Been admitted to the hospital for COVID-19?	[] Yes [] No
0	Been in the Intensive Care Unit due to COVID-19?	[] Yes [] No
0	Needed additional health care (e.g. dialysis, CT scar	n, MRI) as a result of
	COVID-19?	

[] Yes [] No

Is there any context you would like to share about your previous responses? (open text box)

Thank you for sharing this information with the study team. Your Amazon gift card is now available.

If No \rightarrow Thank you for confirming you have not had COVID-19 since we last checked in. Your Amazon gift card is now available.

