Appendix 26: FDA Alert Email

SUBJECT LINE:

Do Not Use Cue Health Device

PREHEADER:

Cue Health's COVID-19 Tests Have a Risk of False Results

BODY COPY:

Dear [FIRST NAME],

This is an alert regarding the ImmunoCARE Study. The U.S. Food and Drug Administration (FDA) issued a communication to recommend that patients, caregivers, and health care providers do not use Cue Health's COVID-19 Tests due to an increased risk of false results.

We are determining next steps for the ImmunoCARE Study. In the meantime, please discontinue use of your Cue Health tests. We thank you for your participation and apologize for any inconvenience this may cause.

Take Care,

The ImmunoCARE Study Team

Questions? Reach out to us at [contact]

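### After a stop over Cue test accuracy, the closure analysis has no rule for infections that rest only on a Cue result, and only the intervention arm was supplied with Cue tests

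*Combined protocol and SAP*

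**What the plan says.** **The stop.** Estimated Duration of Study says the trial ended early "due to the FDA issuing a warning letter regarding Cue Health's COVID-19 test accuracy and calling for discontinuing use of the device in May 2024". The participant email in Appendix 26 passes on the recommendation: "do not use Cue Health's COVID-19 Tests due to an increased risk of false results". Neither text gives an error rate or says whether the errors were false positives or false negatives.

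**The analysis after the stop.** One sentence: "We plan to analyze the data primarily to characterize the effect of the COVID-19 pandemic on the study population". It carries no case definition, no rule for Cue results and no sensitivity analysis.

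**Where cases come from.** The only statement is in Sample Size and Data Analysis: "we should reach a target of 900 confirmed COVID positive cases reported in the survey or claims (approximately 450 per arm". The baseline, monthly and end-of-study surveys in Appendix 3 ask for a yes or no to "Contracted COVID-19". They have no field for test brand or type, confirmatory testing or event date. The closure email in Appendix 28 still asks for the end-of-study survey.

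**Who tests with Cue.** Study Design gives the intervention arm "up to 10 Cue COVID Molecular tests per month for their own" use and for close contacts; controls test as usual. The in-app screens before Appendix 15 ask intervention participants to take a baseline test when the kit arrives, and Appendix 15 schedules reminders for it.

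**Data and harm.** Data Acquisition, Storage and Analysis says: "All study data will be integrated by CareEvolution via the study app and the Cue Health app". Adverse Events says: "We do not expect any adverse events to occur". Risks and Benefits of Participation does not list false results, and no analysis of their consequences is planned.

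**The concern.** The closure analysis describes COVID-19 in a population where one half was given a test whose accuracy ended the trial. Unless a rule is stated, a false-positive Cue result that a participant reports becomes a case, and an infection missed by Cue and not found otherwise becomes a non-case. Controls tested by other means, so the error would differ by arm, and it would also enter any pooled figure.

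Two quantities are exposed. The first is the infection count, which Study Design lists for comparison between arms. The second is severity per infection, which has infections as its denominator. False positives enlarge that denominator without adding admissions, so the intervention arm looks milder per case, which is the direction of the study's hypothesis. False negatives in mild infections do the opposite.

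The plan also does not look at what followed a false-negative result in a high-risk participant, although the introduction says that treatment works best in a short window at disease onset.

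**Working it through.** **1. Reproduce the reference figure, 410 (Table 2, intervention arm, reported positives).**
- Followed after 5% loss: 5,000 × 0.95 = 4,750.
- Control infections over two 4-month periods at 5.9%: 4,750 × (1 − 0.941²) = 544, against 540 stated.
- Intervention infections, 5% fewer: 540 × 0.95 = 513, as stated.
- Reported, after 20% non-reporting: 513 × 0.80 = 410, as stated.

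**2. False positives from one baseline test each (error rates assumed).** The numerator has to carry the same losses as the 410.
- Tested, retained and reporting: 5,000 × 0.95 × 0.80 = 3,800.
- At 1%: 3,800 × 0.01 = 38, and 38/410 = 9%.
- At 2%: 3,800 × 0.02 = 76, and 76/410 = 19%.

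This assumes that everyone takes the baseline test and that every false positive is later reported as an infection. Tests after exposure or symptoms would add to it.

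**3. Effect on severity per infection (false positives alone).** Table 2 expects 68 admissions among the 410.
- No false positives: 68/410 = 16.6%.
- With 38: 68/448 = 15.2%, a relative fall of 1 − 410/448 = 8%.
- With 76: 68/486 = 14.0%, a relative fall of 1 − 410/486 = 16%.

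The planned true effect on this ratio is a 30% relative reduction.

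**4. False negatives (sensitivity assumed 0.80–0.95, all cases found by Cue).** Missed cases: 410 × 0.05 = 21 to 410 × 0.20 = 82. This is the same order as step 2, in the opposite direction.

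**5. Both errors together.** Take the 513 true infections among 4,750 followed, so 4,750 − 513 = 4,237 are uninfected. With sensitivity Se, specificity Sp and k test occasions per uninfected person:

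observed = 513 × Se + 4,237 × (1 − Sp^k)

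| k | Sp | Se | Observed | Observed/true | False share |
|---|---|---|---|---|---|
| 1 | 0.999 | 0.80 | 415 | 0.81 | 1% |
| 1 | 0.99 | 0.80 | 453 | 0.88 | 9% |
| 1 | 0.99 | 0.95 | 530 | 1.03 | 8% |
| 2 | 0.98 | 0.95 | 655 | 1.28 | 26% |
| 4 | 0.95 | 0.95 | 1,273 | 2.48 | 62% |
| 4 | 0.95 | 0.80 | 1,196 | 2.33 | 66% |

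Across the range examined (k from 1 to 4, Sp 0.95–0.999, Se 0.80–0.95) the observed count runs from 0.81 to 2.48 times the true one. The documents supply none of these inputs, so neither size nor direction can be fixed from them.

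**The case against.** **Counting Cue-only cases is not a stated rule.** A reader might infer that the plan says these infections will count. It does not: the closure sentence is silent, and the survey-or-claims wording belongs to the sample-size target. This stands, and the point is therefore about a default. The end-of-study survey still in use cannot separate Cue results from others.

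**Hospitalization, the primary outcome, is not measured by Cue, and uptake is unknown.** Both are true. Intervention participants could also test and seek care elsewhere. But infection rates are a listed comparison, and an account of the pandemic's effect can hardly leave infections out.

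**Safety.** A reader might infer that the trial would close with an unreliable safety conclusion. The documents contain and plan no such conclusion. Stop-use messages were prepared, the study was ended, and general reporting duties remain in place. The consent pages are not in the public text, so nothing can be said about what participants were told of false results. What stands is that no analysis examines their consequences.

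**Excluding Cue-only cases.** A reader might want them out of the headline. That would remove true infections, plausibly the milder ones, from one arm only. Claims connection is optional for immunocompromised participants, so Cue-only would partly mean that no claims were shared. A Cue Care prescription follows a positive Cue result and does not confirm it. This objection stands and shapes the fix.

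**Size.** Dividing 50 or 100 false positives among 5,000 participants by 410 gives 12–24%. That sets a gross numerator against a denominator already reduced for drop-out and non-reporting; 9–19% is the like-for-like figure.

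**Conclusion.** The concern holds as a gap in the closure analysis. The plan does not say how Cue-based case status will be handled, and following it as written leaves infection counts and severity per infection open to arm-differential misclassification. The documents support an increased risk of false results, not that any given result was false.

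The 9–19% is an illustration. It rests on assumed false-positive rates of 1–2%, full uptake of one baseline test, full reporting of false positives as infections, and Table 2's target for full enrolment over 8 months, which a study stopped early may not have reached. False negatives could offset it or reverse it. The case for change is that the size is unknown and can be bounded, not that a particular bias has been shown. Stating the rule and the range is a cheap improvement that affects what the descriptive analysis can conclude.

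**What to change.** Add to Estimated Duration of Study, or to a short closure analysis plan:

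1. **Linkage.** Link Cue app results to survey and claims data. First confirm that results are held by date and user profile; the protocol says data are integrated through the app but does not list individual results.
2. **Case source.** Report infections and severity per infection by arm in three groups: claims diagnosis or non-Cue care; Cue result only; self-report without a Cue result. Do not treat a Cue Care prescription as independent confirmation.
3. **Side-by-side figures.** Show all-case figures next to figures without Cue-only cases, with neither presented as a correction of the other.
4. **Sensitivity analysis.** Recalculate infection counts and severity per infection over a stated range of test sensitivity and specificity, with the source of the range given.
5. **Outcomes after a negative result.** In claims-linked intervention participants, give the number with a COVID-19 ED visit, admission or death after a negative Cue result on their own profile. Present it without causal interpretation: there is no comparator, and the result may have been correct on the day. The surveys carry no event dates, so this cannot extend to survey-only participants.

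**Cost.** Some linkage and analysis work, and no new data collection if result-level Cue data are held. Linkage will be incomplete where claims were not connected or where contacts used the participant's profile, and item 5 covers only the claims-linked subset.

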phone numbers, secondary contacts, and birth dates from participants who cannot share their claims data. Participants and their secondary contacts will only be called at the end of the study, by a research coordinator, to ask participants to complete surveys and remind them about reimbursement opportunities. Participants will be considered lost to follow up after three phone calls. Birth dates will be used to search the national death index.

Outreach

Center for Equitable and Diverse Research (CEDR), a division of the Institute for Public Health at SDSU. CEDR will be involved in conducting in-person outreach and education, study recruitment, and technical assistance as needed to help participants in San Diego County complete study requirements including the 1) eligibility survey, 2) using and navigating the MyDataHelps Web or App including assistance in completing monthly questionnaires, 3) creating the CUE Health App account, 4) completion of the informed consent process, 5) confirmation of immunocompromised status or age and 5) navigation of the CUE Health app.

CEDR will utilize a multi-strategy approach to study recruitment that will use the Community Health Worker/Promotores (CHW/P) model to conduct individual and group outreach and education activities with community members, community clinics, senior centers, and community organizations. Example activities include outreach at health fairs, community clinic waiting rooms, patient groups and senior centers; provider education to generate patient referrals; and partnerships with community-based organizations and advocacy groups to raise awareness with the community members they serve. During all outreach and education activities, prospective study participants will be asked for consent to voluntarily provide their contact information for follow-up calls and text messages to support enrollment and study retention. CEDR will share the IRB-approved outreach one-pager found in Appendix 4 with interested participants which will include the CEDR email address and phone number for those who have questions about the study. Talking points for use by outreach staff while speaking with participants about the study can be found in Appendix 25.

Risks and Benefits of Participation

The risks of participating in this study are minimal.

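### The only formal exit described is withdrawal of consent, which ends all data collection; no option keeps passive follow-up for hospitalization, and it is unclear whether the three-month claims rule covers people who withdraw

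*Combined protocol and SAP*

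**What the plan says.** The Participant Withdrawal section ties its rule to consent: "A participant who wishes to withdraw consent can make a request through the app during the study period". Data gathered before that point are kept: "Any data that has been entered in the database will be included in the analysis of the study". Nothing is gathered afterwards: "All study activities and data collection will stop at the time of withdrawal". The section describes no intermediate level.

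The Estimated Duration of Study section, which also announces the early closure, says of claims: "If connected, claims data collection will persist for about three months after participation ends". It does not mention withdrawal.

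On outcome sources, Study Design says: "The primary outcome will be the number of hospitalizations that will be assessed from survey and claims data". Sample Size and Data Analysis names the survey alone ("The number of hospitalizations will be assessed based on survey data") and assumes that at least 80% complete the final one. For deaths, the Surveys section adds, for participants who cannot share claims: "Birth dates will be used to search the national death index". Table 2 allows 5% per arm under the row "Loss to follow-up / drop-out / failure", with no separate figure for withdrawal.

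**The concern.** The trial asks whether offering tests, telemedicine and drug delivery lowers hospitalization. That comparison needs outcomes from everyone randomized, including people who give up the package. A connected claims feed needs no further effort from the participant, and one final survey covers the whole period since enrolment. A participant who wants no more contact need not also be lost for the primary outcome, yet the only formal exit described has that effect.

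The trial is open, and reasons for leaving could differ by arm. Only the intervention arm has an account to set up, kits to order and reorder prompts. The risk section expects some controls to be disappointed, although it does not link this to leaving. The Reimbursement section reports that an interim look found claims better balanced between arms than survey data, and it adds a payment to obtain more claims. Ending claims capture at withdrawal works against that remedy.

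**Working it through.** **1. What triggers the rule.**
- Participant Withdrawal: the trigger is a request to withdraw consent.
- Study Interventions and Cue Care: testing is asked for only after exposure or symptoms, and telehealth is optional.
- Reimbursement: people without claims who miss monthly surveys may be offered half of the missed payment for completing the final survey.
- Surveys: people who cannot share claims count as lost only after three calls at the end of the study.
- Appendix 3: the End of Study Survey asks about hospital admission since enrolment.

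So non-use and missed surveys leave a person in follow-up. Only formal withdrawal ends it.

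**2. The two claims sentences.** The three-month rule starts when participation ends and stands under study duration. The stop rule starts at withdrawal and stands under its own heading. They fit together if the first means study end and the second means withdrawn consent. However, the withdrawal paragraph opens by speaking of a participant who discontinues participation, so the two starting points overlap. For a claims-linked person who withdraws, the text does not say which rule applies.

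**3. The plan's own figures.** Hospitalization per case in control is 0.75 × 0.28 + 0.25 × 0.10 = 0.235. In the intervention arm it is 0.235 × 0.7 = 0.1645. Table 2's reported cases give 432 × 0.235 = 101.5 (printed as 102) and 540 × 0.95 × 0.8 × 0.1645 = 67.5 (printed as 68). The planned difference is 102 − 68 = 34. With 450 cases per arm, a two-sided 0.05 test of two proportions (pooled normal approximation) has power 0.754, against 0.76 stated.

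**4. Loss unrelated to risk and equal in both arms.** Assume the 450 cases already allow for 5% loss. At 10% loss, 450 / 0.95 × 0.90 = 426 cases per arm, and power is 0.731. At 15% loss there are 403 cases and power is 0.707. Each further 5 points of loss costs 2 to 3 points of power.

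**5. Loss related to risk and unequal between arms.** The documents give no withdrawal rate and no risk for people who withdraw. This is an illustration under stated assumptions, not an estimate.
- Assumption: all 5% loss is formal withdrawal, so 0.05 × 5,000 = 250 per arm. This is an upper bound, because the row combines several kinds of loss.
- Eight-month risk, control: 0.059 × 2 × 0.235 = 2.77%.
- Eight-month risk, intervention: 0.059 × 2 × 0.95 × 0.1645 = 1.84%.
- At average risk, 250 people carry 6.9 (control) and 4.6 (intervention) hospitalizations.
- Assumption: threefold risk, in intervention leavers only. They carry 13.8, an extra 13.8 − 4.6 = 9.2.
- The 34 is in reported events, so the same 20% non-reporting must be applied: 9.2 × 0.8 = 7.4, or 22% of 34.
- That treats everyone as leaving at the start. If exits are spread evenly (assumption) and earlier admissions are already recorded, half of the risk is lost: 7.4 / 2 = 3.7, or 11% of 34.

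Losing these events from the intervention arm would make the package look better than it is. If only control leavers had threefold risk, the bias would reverse: 6.9 × 2 × 0.8 = 11.0 events, or 5.5 with even exits. If both arms had the same excess, 20.8 and 13.8 events would be carried away, nearly the same ratio as 6.9 to 4.6, and the relative effect would be essentially undisturbed.

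**The case against.** Stopping collection when consent is withdrawn protects the participant and is legitimate, and earlier data are retained. That stands: the lack of an express partial option is a weakness of design, not an error.

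A reader might infer that anyone who merely tires of the device or the surveys is lost for the primary outcome. The documents do not support this. Such people remain reachable through the final survey, through phone calls if they cannot share claims, and through claims where connected.

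A reader might also infer that the two claims sentences give opposite instructions. They do not. They stand under different headings and can be reconciled. What remains is an ambiguity.

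A third tempting reading sets 9.2 events against 34 and concludes that about a quarter of the effect is at risk. That mixes unreported with reported events, puts every exit at the start, counts all loss as withdrawal, and needs a one-arm threefold risk that nothing in the documents supports.

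Three limits also stand. The consent pages were not available for review, so a partial option there cannot be excluded. The death index yields no hospitalizations, so for people without claims, follow-up without contact recovers no primary-outcome data. And the study closed early after the FDA warning, with its data now meant mainly to describe the pandemic's effect on this population, so a new screen cannot recover past withdrawals.

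**Conclusion.** The point holds in limited form. The protocol describes a single formal exit and ends all collection there, so a person who withdraws but would have allowed passive follow-up supplies no later hospitalizations. Whether the three-month claims rule reaches such a person is unsettled.

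The size cannot be computed from the documents. With all 5% loss taken as withdrawal and threefold risk in intervention leavers only, it is about 4 to 7 reported events against a planned difference of 34. The lower end assumes evenly spread exits and the upper end assumes exit at the start. Fewer withdrawals or similar risk in both arms would make it smaller. The direction is unknown. The change is worth making because it is cheap and protects the source that the trial's own interim look found better balanced, but early closure limits what it can now achieve.

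**What to change.** Replace the single exit with three choices in the withdrawal request:

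- (a) stop study activities, but keep the claims link and the final survey;
- (b) stop all contact, but keep the passive claims link where connected, plus a death-index search for deaths only;
- (c) withdraw consent for all further collection.

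Analyse people who choose (a) or (b) in their randomized arm. State that the three-month claims rule applies to (a) and (b) and not to (c). For withdrawals that have already happened, state which rule governs their claims, and report their number and timing by arm.

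The cost is revised protocol and consent wording and one extra screen. Participants must be told plainly that passive follow-up continues unless they choose (c). The benefit is confined to remaining claims follow-up or any continued protocol.
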